a) Analysis Plan: The first aim of this proposal is to determine whether vitamin D₃ supplementation, compared to placebo, is more effective in maintaining stable or lowered number of positive cores and Gleason score, assessed by the pathologist as per standard of care. Baseline and end-of-study biopsy will be compared in each patient by calculating the change in number of positive cores and the change in Gleason score. These will be described using summary statistics of the ordinal changes and graphical displays. Each patient will also be categorized using three binary indicators: (1) stable Gleason (better or the same score as baseline) vs. worse Gleason (higher Gleason score); (2) stable number of cores (fewer or the same number of positive cores) vs. higher number of cores (more positive cores than at baseline; (3) stable pathology, as defined in Table 1. In each arm of the study and for each outcome, the proportions will be estimated with 95% confidence intervals. Arms will be compared using Fisher's exact test with a 1-sided alpha of 0.05. We will focus on stable number of cores and stable pathology as we expect that there will be less significant changes in Gleason scores. The second aim focuses on additional treatment after the end-of-study biopsy. We will estimate the proportion of men in each group who go on to hormone therapy, prostatectomy, or radiation therapy along with their 95% confidence intervals. We will also compare the proportions across groups using a Fisher's exact test with 2-sided alpha of 0.05.

For aim 3, serum levels of PSA and 25(OH)D will be measured at baseline and every 16 weeks until the end of the study; cholecalciferol, 1,25(OH)₂D, and PTH will be measured at baseline and at the end of the study. Graphical displays will be created to show the trends by patient over time in each group. Linear longitudinal modeling will be used to estimate trajectories over time in each group and to estimate changes from baseline to each relevant time point. Slopes will be estimated and tested for differences from zero in each group. We also plan to compare slopes across groups. Associations between changes in each of these levels with changes in Gleason, number of positive cores, and need for definitive surgery will be estimated using logistic regression models (with pathology outcomes defined above as the outcome measures).

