For aim 4, the expression of VDR, CYP27B1, p21, TGFβ, COX-2, and NFκB will be assessed by immunohistochemistry in pre- and post-treatment biopsy tissue specimens. As stated above, assessment of the intensity of the immunohistochemical staining (from negative to 4+) will be performed by the collaborating Pathologist, [name], who will be blinded to the randomization.

b) Sample Size Justification: The sample size was determined based on the ability to detect significant differences in the proportion of subjects with stable number of cores and stable pathology outcomes. Our assumptions regarding null and alternative hypothesis are based on our preliminary data from our single arm study of men receiving an intervention of vitamin D₃ alone with very similar inclusion/exclusion criteria. Our null hypothesis is that both arms will have 40% of men with stable number of cores, and our alternative is that the vitamin D₃ arm will have 70% of men with stable cores (and 40% in the placebo arm). Using a 2-sided alpha of 0.05, we have 87% power to detect this difference with 58 men per arm. Based on our preliminary data there are relatively few men who have an increase in Gleason without an increase in the number of positive cores, so we use the same sample size calculation to power the comparison of proportions of number of men with stable pathology. Examining trends in historical data and our previous study, we would expect 15% of men in the treatment arm to have additional treatment after repeat biopsy, compared to 40% in the placebo arm. This difference can be detected with 81% power - alpha of 0.05. From our earlier studies, we anticipate that some patients will drop out of the study, making them inevaluable for the primary endpoints which require end-of-study biopsy results. As such, we will enroll 68 patients per arm to ensure at least 58 evaluable patients per arm (i.e, allowing 15% dropout). This is a conservative estimate but consistent with previous experience. Aims 3 and 4 are secondary and, as such, power is not provided. Hypothesis testing across groups is not planned for these aims.

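### Aims 1 and 2 carry four unadjusted, unordered tests and an inconsistently implied primary; if any one counts as benefit, the false-benefit rate is about 6–9%

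*Combined protocol and SAP*

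**What the plan says.** For Aim 1, D.6 a) states: "Each patient will also be categorized using three binary indicators". The three are stable Gleason score, stable number of positive cores, and stable pathology as defined in Table 1. It continues: "In each arm of the study and for each outcome, the proportions will be estimated with 95% confidence intervals". The test follows: "Arms will be compared using Fisher's exact test with a 1-sided alpha of 0.05". Two of the three are then emphasised: "We will focus on stable number of cores and stable pathology as we expect that there will be less significant changes in Gleason scores". For Aim 2, the proportions having additional treatment are also tested: "We will also compare the proportions across groups using a Fisher's exact test with 2-sided alpha of 0.05".

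Three places bear on which test is primary, and they differ:

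- D.5 is headed in the singular (Measurement of Primary Outcome) and points to Table 1, a three-level class of response, stable disease or progression.
- D.6 a) lists stable pathology as one of three indicators and puts two of them in focus.
- D.6 b) states its hypotheses for cores ("Our null hypothesis is that both arms will have 40% of men with stable number of cores") and reuses that calculation for stable pathology. It powers Aim 2 separately and describes dropout as "making them inevaluable for the primary endpoints which require end-of-study biopsy results", in the plural. It then says: "Aims 3 and 4 are secondary and, as such, power is not provided". Aim 2 is given no rank.

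Neither part of D.6 gives a testing order, an alpha split, an adjustment or a rule for declaring success.

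**The concern.** With four tests, no order and no consistently named primary, the plan does not say which result decides the trial. Two things follow. The chance that at least one test is falsely significant exceeds that of any single test. The choice of headline also stays open until the data are seen.

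The second risk is practical. In the pilot described under Preliminary Studies, the same 44 treated men and 19 historical controls gave p=0.05 for progression and p=0.025 for response. Rebuilding the counts (15/44 v 12/19 progressed; 24/44 v 4/19 improved), Fisher's test gives 0.051 and 0.026. Two ways of splitting one three-level outcome fell on opposite sides of 0.05. The Concluding Remarks expect this trial to be definitive, so the deciding test should be fixed in advance.

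**Working it through.** **Inputs from the documents (D.6):** 58 evaluable men per arm; Fisher's exact test; one-sided 0.05 for three Aim 1 indicators; two-sided 0.05 for Aim 2; 40% stable cores under the null; planned effects of 70% v 40% (cores) and 15% v 40% (treatment).

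**Inputs that are assumed:** the rates of Gleason rise and the link from pathology to treatment, which the documents do not give. One rough anchor exists. Historical controls had 21% + 16% = 37% improved or unchanged on pathology, against 40% assumed stable on cores, so the Gleason rise among core-stable men would be about 1 − 37/40 = 7.5%. D.6 b) says such men are relatively few.

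**Step 1: the plan's own figures.** Fisher power was enumerated over all pairs of binomial counts at 58 per arm.

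- Cores, 70% v 40%, two-sided 0.05: 87.6% (plan: 87%).
- Aim 2, 15% v 40%, two-sided 0.05: 82.6%, or 81.1% by the continuity-corrected normal formula (plan: 81%).

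Both reproduce. At the one-sided 0.05 of D.6 a), the first becomes 93.8%.

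**Step 2: crude ceiling.** Four independent tests at exactly 5% would give 1 − 0.95⁴ = 18.5%. That is far too high here, for two reasons. Fisher's test is conservative: its true one-sided size at 40% v 40% is 3.6%. The outcomes also overlap.

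**Step 3: simulation under no effect.** There were 200,000 trials per row. Each man has stable cores with probability 0.40. His Gleason score rises with probability g1 if cores are stable and g2 if not. Stable pathology means stable cores and no Gleason rise (response or stable disease in Table 1). He has additional treatment with probability t1 if pathology is stable and t2 if not. Example, row B: stable pathology 0.40 × 0.95 = 0.38; stable Gleason 0.40 × 0.95 + 0.60 × 0.80 = 0.86; treated 0.38 × 0 + 0.62 × 0.645 = 0.40.

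| Row | g1, g2 | t1, t2 | Two focus tests | Focus + Aim 2, benefit only | All four, benefit only | All four, Aim 2 either way |
|---|---|---|---|---|---|---|
| A | 0.02, 0.08 | 0, 0.60 | 4.1% | 5.0% | 6.5% | 8.1% |
| B | 0.05, 0.20 | 0, 0.645 | 4.4% | 5.2% | 7.8% | 9.3% |
| C | 0.10, 0.10 | 0.25, 0.50 | 4.7% | 6.0% | 8.5% | 9.9% |
| D | 0.10, 0.30 | 0.40, 0.40 | 4.7% | 6.1% | 8.7% | 10.2% |
| E (stress) | 0.30, 0.40 | 0.40, 0.40 | 5.4% | 6.9% | 9.6% | 11.0% |

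Row E is a stress case: a 30% Gleason rise among core-stable men fits poorly with D.6 b). A wider grid of 120 settings, with stable cores at 40–70%, gave 6.7–10.8% for all four tests in either direction and 3.9–5.6% for the two focus tests.

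**Step 4: where the excess arises.** In row B the two focus tests give 4.4%. Adding Gleason gives 7.0%, and adding benefit-direction Aim 2 results gives 7.8%. Without Gleason, focus plus Aim 2 benefit is 5.2%. The Gleason test therefore contributes most of the excess.

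**Step 5: dependence on Fisher.** With uncorrected normal tests, row B rises to 11.8% (benefit only) and 14.1% (either direction). The modest figures rely on Fisher's conservatism.

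**Step 6: one primary test.** For stable pathology alone at one-sided 0.05, the true Fisher size is about 3.5% when 38% are stable, and about 3.1–4.0% over the grid.

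**The case against.** The strongest reply has four parts.

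- **A primary is signalled.** D.5 has a singular heading tied to Table 1, and D.6 b) links its primary endpoints to the repeat biopsy, which most naturally means Aim 1. This stands in part. A reader might infer that the plan names no primary at all, and D.5 does not support that. The sounder reading is that the primary is implied inconsistently, because D.6 does not make stable pathology the deciding test.
- **The focus indicators barely inflate error.** This stands. At about 4–6% they are close to nominal, and D.6 a) openly expects little from Gleason. But emphasis does not withdraw the Gleason test or give Aim 2 a rank.
- **Counting any of four as success is not written down.** This also stands. Specific Aims words the hypothesis jointly (cores, Gleason and less treatment) and lists Aims 1 and 2 as separate questions. Controlling error within each aim is a defensible convention. The 6–9% is therefore conditional on a reading that the plan leaves open.
- **The assumed rates drive the number.** True, which is why a range is given.

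A reader might also infer that false benefit claims run at 9–11%. That range includes Aim 2 results showing more treatment on vitamin D, which cannot support a benefit claim. The 18.5% from independent tests is likewise not this plan's error rate.

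**Conclusion.** The point holds as a gap in the testing rules with a moderate effect on error. The four tests have no order or adjustment, and D.5, D.6 a) and D.6 b) imply different primaries. If any of the four were taken as benefit, the false-benefit rate under no effect would be about 6–9%, or about 8–11% counting Aim 2 in either direction. This rests on 58 per arm, Fisher tests as planned, 40% stable cores, and assumed Gleason-upgrade and treatment rates. The two focus indicators alone stay near 4–6%. The documents do not show that the sponsor intends to claim success on any single test; they only fail to rule it out. The plan should be changed, but the fault does not by itself invalidate the design.

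**What to change.** In D.6 a):

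1. Name stable pathology (response or stable disease in Table 1) as the single primary test, consistent with D.5.
2. State one alpha and sidedness, and make D.6 a) and D.6 b) agree. At present the analysis is one-sided 0.05 and the sample size two-sided 0.05. Keeping two-sided 0.05 leaves Fisher power at about 88% for 70% v 40% with 58 per arm.
3. Test the other three in one pre-specified order chosen by the sponsor, each only if the one before is significant. Stable cores, then Aim 2, then Gleason is one example; it keeps the outcome that drives the sample size next to the primary. After a failure, report the remaining outcomes as estimates with confidence intervals and no significance claim.
4. Use the same term for the primary in D.5, D.6 a) and D.6 b).

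This holds the overall error at or below the chosen alpha with no change in sample size. By comparison, Bonferroni over four tests (0.0125 each, sidedness as planned) would cut power to about 81% for 70% v 40% and 64% for Aim 2. The cost is a few sentences and one real loss: later endpoints, including core count and additional treatment, cannot be claimed as confirmatory if an earlier one fails.

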 - Decision Making about Prostate Biopsy survey results
 - Pre-study prostate biopsy report results (Gleason score of positive cores; number of positive cores and percent involvement)
 - Repeat prostate biopsy results (Gleason score of positive cores; number of positive cores and percent involvement)
 - Prostate tissue biomarkers
 - · Blood and urine biomarkers

b) Frequency of monitoring:

- Baseline data (date of birth, race, PSA results, pre-study prostate biopsy results, etc. for inclusion/exclusion determination) will be obtained by the CRC at the screening visit.
- The safety labs and vitamin D levels will be obtained at baseline and every 16 weeks until the exit visit.
- Allostatic load parameters will be obtained at baseline and final study visits
- Decision Making about Prostate Biopsy survey will be completed at baseline and final visit
- Repeat prostate biopsy results and the prostate cancer treatment plan will be obtained by the CRC and entered in the de-identified data spreadsheets.
- Study endpoints will be evaluated by the PI and Co-Investigators who will be blinded to the subject randomization.
- c) Adverse Event Reporting:

Internal Adverse Events and Serious Adverse Events related to the study medication will be reported to the corresponding VAMC/MUSC IRB, VA R&D and FDA, within the required time period, as soon as discovered and documented. The Clinical Investigator will communicate with the subject's Primary Care Provider (or team) describing the adverse event to insure continuity of care is initiated/scheduled.

F. BIBLIOGRAPHY & REFERENCES CITED

- **1.** http://www.cancer.org/docroot/CRI/content/CRI 2 4 1X What are the key statistics for prostate cancer 36.asp
- 2. Schwartz GG. Vitamin D and the Epidemiology of Prostate Cancer. Semin Dial, 18: 276-289, 2005.
